6.1 Dose Levels, Dose Escalation, Sample Size and Justification of the Dose

6.1.1 Dose Levels, Dose Escalation and Sample Size

The dose levels to be used in assessing the safety and anti-cancer activities of CPI-613 in 10 patients with advanced bile duct cancers will be determined from a dose-escalation scheme using cohorts of patients with advanced bile duct cancers, as described below. The dose-escalation scheme is based on the number of patients exhibiting dose-limiting toxicity (DLT), and DLT is defined as toxicity of Grade 3 or higher attributed as probably or definitely related to CPI-613. The DLT determining period for all cohorts in the dose-escalation scheme is through the first cycle.

Comprehensive Cancer Center of Wake Forest University
A Pilot Study: Open-Label Clinical Trial of CPI-613 in Patients with Advanced Bile Duct
Cancers
CCCWFU # 59212

Cohort 1: The first 3 patients will not be treated with the 5 daily doses of CPI-613 during the pre-Cycle 1 week, and will only be treated with 3-weeks-on-1-week-off treatment cycles (see Table 6-1). The dose of CPI-613 will be 2,300 mg/m² (which is approximately three-quarters of the target dose). If none of these 3 patients develop a dose-limiting toxicity (DLT) through Cycle 1, the dose for the 3-weeks-on-1-week-off treatment cycles will be 3,000 mg/m² in all subsequent patients in this trial. However, if a DLT is observed in a patient (whether it is the 1st, 2nd or 3rd of the 3 intended patients), the number of patients in this cohort will be expanded to a maximum of 6 patients. If no DLT is observed in another patient out of a maximum of 6 patients, the dose for the 3-weeks-on-1-week-off treatment cycles will be 3,000 mg/m² in all subsequent patients in this trial. However, once DLT is observed in 2 patients, no additional patients will be treated at 2,300 mg/m² for the 3-weeks-on-1-week-off treatment cycles from that point on, even though the total number of patients in this cohort is as few as 2. The dose level of 2,300 mg/m², which induces a DLT in 2 or more patients, is considered to be above the maximum tolerated dose (MTD) for the 3-weeks-on-1-week-off treatment cycles. In this case, all subsequent patients in this trial will be treated at 1,700 mg/m² for the 3-weeks-on-1-week-off treatment cycles.

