Cohort 4: This cohort will be performed only if DLT is observed in 1 or less patients in Cohort 3. There are 3 patients in this cohort, and the dose of CPI-613 for the 3-weeks-on-1-week-off treatment cycles will be as determined from Cohort 1. The dose for the 5 daily IV infusions during the pre-Cycle 1 week will be 3,000 mg/m²/day. If none of these 3 patients develop a DLT, the study can move onto Cohort 5. However, if a DLT is observed in a patient (whether it is the first, second or third of the 3 intended patients), the number of patients in this cohort will be expanded to a maximum of 6 patients. If no DLT is observed in another patient out of a maximum of 6 patients, the study will move onto Cohort 5. However, if a DLT is observed in 2 patients, no additional patients will be treated at 3,000 mg/m²/day during the pre-Cycle 1 week even though the total number of patients at this cohort is as few as 2. The dose level of 3,000

Comprehensive Cancer Center of Wake Forest University
A Pilot Study: Open-Label Clinical Trial of CPI-613 in Patients with Advanced Bile Duct
Cancers
CCCWFU # 59212

mg/m²/day during the pre-Cycle 1 week, which induces a DLT in 2 or more patients, is considered to be above the MTD for the pre-Cycle 1 week. In this case, the dose of CPI-613 for the pre-Cycle 1 week in subsequent patients in this trial will be 2,300 mg/m²/day

Cohort 5: This cohort is performed once the dose of CPI-613 for the 3-weeks-on-1-week-off treatment cycles has been determined from Cohort 1, and once the dose of CPI-613 for the pre-Cycle 1 week has been determined from Cohort 2-4. There are 10 patients in this cohort. These patients will be treated with CPI-613 for 5 days during the pre-Cycle 1 week at doses as determined from Cohorts 2-4, and the dose of CPI-613 for the 3-weeks-on-1-week-off treatment cycles will be as determined from Cohort 1.

6.1.2 *Justification of the Dose*

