For adverse events unrelated to serum creatinine elevation or reduction in renal function but are possibly related to CPI-613, the occurrence of Grade 1 toxicity does not generally require dose modification for subsequent doses for that patient. However, if Grade 2 toxicity (other than alopecia and nausea) probably related to CPI-613 develops, treatment is to be withheld and can resume only after the Grade 2 toxicity has been reduced to Grade 1 or below, and the dose level for subsequent doses for that patient will be reduced by 25% of the dose at which such Grade 2 toxicity occurs. Grade 2 alopecia and nausea do not require withholding treatment or dose reduction. If Grade 3 or 4 toxicity probably related to CPI-613 develops, dosing of CPI-613 of that patient will be withheld and the patient shall be monitored for recovery from, and reversibility of, such Grade 3 or 4 toxicity. To resume treatment with CPI-613 for a patient who has had CPI-613-related Grade 3 or 4 toxicity, the Grade 3 or 4 toxicity must be reduced to Grade 1 or below, and the dose level for subsequent doses for that patient will be reduced to 50% of the dose at which such Grade 3 or 4 toxicity occurs.

For adverse events related to creatinine elevation or reduction in renal function that are possibly related to CPI-613, dosing of the patient will be withheld even if the severity level is Grade 2 or above. Treatment can resume only after the toxicity has been reduced to Grade 1. The dose level for subsequent doses for that patient will be reduced by 15% if the severity level is of Grade 1, by 25% for Grade 2 toxicity, and by 50% for Grade 3 or 4 toxicity.

Furthermore, if the toxicity possibly related to CPI-613 is acute renal failure and the severity level is Grade 3 or 4, further patient enrollment will be temporarily suspended in order to enable assessment of the following aspects of the trial and implementation of corrective measures or protocol amendment, and if necessary:

- compliance of the study sites and investigators to the study protocol
- evaluation of the appropriateness of the procedures for monitoring renal function

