8.0 ADVERSE EVENTS LIST AND REPORTING REQUIREMENTS

8.1 Adverse Event Characteristics

- **CTCAE term (AE description) and grade:** The CTEP Active Version of the NCI Common Terminology Criteria for Adverse Events (CTCAE 4.0) will be utilized for AE reporting. The CTEP Active Version of the CTCAE is identified and located on the CTEP website at http://ctep.cancer.gov/protocolDevelopment/electronic_applications/ctc.htm. All appropriate treatment areas should have access to a copy of the CTEP Active Version of CTCAE.
- **‘Expectedness’:** AEs can be ‘Unexpected’ or ‘Expected’ (see Section 7.1 above) for expedited reporting purposes only.
- **Attribution of the AE:**
 - Definite – The AE *is clearly related* to the study treatment.
 - Probable – The AE *is likely related* to the study treatment.
 - Possible – The AE *may be related* to the study treatment.
 - Unlikely – The AE *is doubtfully related* to the study treatment.
 - Unrelated – The AE *is clearly NOT related* to the study treatment.

List of Adverse Events to be Reported:

Comprehensive Cancer Center of Wake Forest University
A Pilot Study: Open-Label Clinical Trial of CPI-613 in Patients with Advanced Bile Duct
Cancers
CCCWFU # 59212

*Abdominal pain
Alkaline phosphatase
ALT (SGPT)
Anorexia
AST (SGOT)
Bilirubin (hyperbilirubinemia)
Calcium (hypercalcemia, hypocalcemia)
*Creatinine
*Diarrhea
Flushing
Hemoglobin (anemia)
*Injection site Reaction
Leukocytes
Lymphopenia
*Nausea
Neutrophils (neutropenia)
Platelets (thrombocytopenia)
Potassium
Sodium
*Vomiting

All grade 3, 4, 5 adverse events should be reported on flowsheets and in ORIS regardless of whether they are on this list.

Asterisk (*) denotes expected Adverse Events.

All Serious Adverse Events (SAEs) which are Possibly, Probably or Definitely Related to CPI-613, and Unexpected are required to be reported to Cornerstone Pharmaceuticals via the provided SAE Reporting Form within 7 days. All completed forms must be sent to [name] at Cornerstone. Cornerstone will submit any applicable SAEs to the FDA.

SAE reports must be submitted to Cornerstone by fax or email to the following address:

Department of Regulatory and Clinical Affairs
Cornerstone Pharmaceuticals, Inc.
[name]
[name]
[contact]
Telefax: [contact] Email: [contact]

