8.3 WFUHS IRB AE Reporting Requirements

Any unanticipated problems involving risks to subjects or others and adverse events shall be promptly reported to the IRB, according to institutional policy. Reporting to the IRB is required regardless of the funding source, study sponsor, or whether the event involves an investigational or marketed drug, biologic or device. Reportable events are not limited to physical injury, but include psychological, economic and social harm. Reportable events may arise as a result of drugs, biological agents, devices, procedures or other interventions, or as a result of questionnaires, surveys, observations or other interactions with research subjects.

All members of the research team are responsible for the appropriate reporting to the IRB and other applicable parties of unanticipated problems involving risk to subjects or others. The Principal Investigator, however, is ultimately responsible for ensuring the prompt reporting of unanticipated problems involving risk to subjects or others to the IRB. The Principal Investigator is also responsible for ensuring that all reported unanticipated risks to subjects and others which they receive are reviewed to determine whether the report represents a change in the risks and/or benefits to study participants, and whether any changes in the informed consent, protocol or other study-related documents are required.

Any unanticipated problems involving risks to subjects or others occurring at a site where the study has been approved by the WFUHS IRB (internal events) must be reported to the WFUHS IRB within 7 calendar days of the investigator or other members of the study team becoming aware of the event.

Any unanticipated problems involving risks to subjects or others occurring at another site conducting the same study that has been approved by the WFUHS IRB (external events) must be reported to the WFUHS IRB within 7 calendar days of the investigator or other members of the study team becoming aware of the event.

Any event, incident, experience, or outcome that alters the risk versus potential benefit of the research and as a result warrants a substantive change in the research protocol or informed consent process/document in order to insure the

Comprehensive Cancer Center of Wake Forest University
A Pilot Study: Open-Label Clinical Trial of CPI-613 in Patients with Advanced Bile Duct
Cancers
CCCWFU # 59212

safety, rights or welfare of research subjects.

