9.0 STATISTICAL CONSIDERATIONS

This is a pilot study with the primary goal to be able to determine initial estimates of RR, and secondary goals to determine PFS and OS. Data from this trial will also provide additional data concerning the safety profile of the CPI-613 therapy. Since there is some uncertainty about what dose to examine for the 10 patients in this pilot study we propose the following pre-defined dose escalation scheme in order to determine the appropriate dose to provide to 10 patients with advanced bile duct cancers. This scheme has been discussed/proposed by the FDA and it is very specific and is described below. The dose-escalation scheme is based on the number of patients exhibiting dose-limiting toxicity (DLT), and DLT is defined as toxicity of Grade 3 or higher. The DLT determining period for all cohorts in the dose-escalation scheme is through the first cycle. Note – this section is redundant with section 6.1 but is included for completeness.

Cohort 1: The first 3 patients will not be treated with the 5 daily doses of CPI-613 during the pre-Cycle 1 week, and will only be treated with 3-weeks-on-1-week-off treatment cycles (see Table 6-1). The dose of CPI-613 will be 2,300 mg/m² (which is approximately three-quarters of the target dose). If none of these 3 patients develop a dose-limiting toxicity (DLT) through Cycle 1, the dose for the 3-weeks-on-1-week-off treatment cycles will be 3,000 mg/m² in all subsequent patients in this trial. However, if a DLT is observed in a patient (whether it is the 1st, 2nd or 3rd of the 3 intended patients), the number of patients in this cohort will be expanded to a maximum of 6 patients. If no DLT is observed in another patient out of a maximum of 6 patients, the dose for the 3-weeks-on-1-week-off treatment cycles will be 3,000 mg/m² in all subsequent patients in this trial. However, once DLT is observed in 2 patients, no additional patients will be treated at 2,300 mg/m² for the 3-weeks-on-1-week-off treatment cycles from that point on, even though the total number of patients in this cohort is as few as 2. The dose level of 2,300 mg/m², which induces a DLT in 2 or more patients, is considered to be above the maximum tolerated dose (MTD) for the 3-weeks-on-1-week-off treatment cycles. In this case, all subsequent patients in this trial will be treated at 1,700 mg/m² for the 3-weeks-on-1-week-off treatment cycles.

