even though the total number of patients at this cohort is as few as 2. The dose level of 3,000 mg/m²/day during the pre-Cycle 1 week, which induces a DLT in 2 or more patients, is considered to be above the MTD for the pre-Cycle 1 week. In this case, the dose of CPI-613 for the pre-Cycle 1 week in subsequent patients in this trial will be 2,300 mg/m²/day

Cohort 5: This cohort is performed once the dose of CPI-613 for the 3-weeks-on-1-week-off treatment cycles has been determined from Cohort 1, and once the dose of CPI-613 for the pre-Cycle 1 week has been determined from Cohort 2-4. There are 10 patients in this cohort. These patients will be treated with CPI-613 for 5 days during the pre-Cycle 1 week at doses as determined from Cohorts 2-4, and the dose of CPI-613 for the 3-weeks-on-1-week-off treatment cycles will be as determined from Cohort 1.

As can be seen by the above scheme there are several possible scenarios that could occur in order to determine the dose for the 10 patients to be evaluated in the pilot trial. Once the above procedure is completed we will then enroll 10 patients at the determined dose.

Accrual Rate

We anticipate accruing one patient per month for this protocol. Since the dose escalation procedure described above may involve a variable number of patients (at least 6 but possibly more) we cannot be certain the entire length of accrual for this protocol. However, we do anticipate that the total number of patients in this protocol will be between 16-40 (with 16-22 being the most likely range). Thus, we anticipate that we will reach the target sample size of 10 patients treated at MTD within two years. A minimum of 16 patients to a maximum of 40 patients will be accrued to the study, with the first 6-30 being evaluated for toxicity in a dose-escalated manner for determining the MTD, and the remaining 10 used in the analytic sample.

Proposed Analyses

The analyses for this protocol will be primarily descriptive. With a sample size of 10 treated at MTD, we do not expect to see statistically significant effects for the outcomes of interest, however this data will provide useful preliminary data on the overall safety and efficacy of CPI-613 and provide useful data to predict the variability and likely effect sizes for these outcomes.

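### The automatic enrolment suspension for acute renal failure in Section 6.2 names Grade 3 or 4 only, so a renal death graded only as Grade 5 does not trigger it as worded

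*Combined protocol and SAP*

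**What the plan says.** Section 6.2 contains the plan's only automatic suspension of enrolment. It applies when a toxicity possibly related to CPI-613 is "acute renal failure and the severity level is Grade 3 or 4, further patient enrollment will be temporarily suspended". The stated purpose is to review site and investigator compliance and the adequacy of renal monitoring, and to correct or amend as needed.

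The protocol treats Grade 5 as a grade of its own. Section 8.1 says "All grade 3, 4, 5 adverse events should be reported on flowsheets and in ORIS", the STRC table in Appendix B gives Grade 5 its own columns, and the adverse event log in Appendix C has a separate box for death.

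For dose escalation, Section 6.1.1 says "DLT is defined as toxicity of Grade 3 or higher attributed as probably or definitely related to CPI-613" and "The DLT determining period for all cohorts in the dose-escalation scheme is through the first cycle". Section 9.0 repeats the definition with the same grade threshold and the same period, but with no attribution condition.

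**The concern.** The sentence protects patients who have not yet started. Its purpose is to let someone check renal monitoring and protocol compliance before another patient is exposed. A death from renal failure is the strongest reason for that check, yet as worded it is the one severe outcome that the trigger leaves out.

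Elsewhere in Section 6.2 the restriction to Grades 3 and 4 is harmless. Those sentences govern withholding, resuming or reducing a patient's own dose, where Grade 5 has no application. The suspension sentence appears to carry the same grade range into a setting where Grade 5 does matter.

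Safety is a primary outcome of the trial (Section 2.2). At stake is whether the pause after a possibly related renal death is guaranteed or depends on a judgement made at the time.

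**Working it through.** This is mainly a check of text against text. The plan states no figure to reproduce.

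**Step 1. What triggers the suspension.** For acute renal failure possibly related to CPI-613:

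| Grade | Section 6.2 as worded | With Grade 3 or higher |
|---|---|---|
| 1 | no | no |
| 2 | no | no |
| 3 | yes | yes |
| 4 | yes | yes |
| 5 | not named | yes |

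**Step 2. Whether the protocol's grade ranges normally include death.** Where the text means an open upper end, it says so. The DLT definition starts at Grade 3 and is open above (Sections 6.1.1 and 9.0). The renal dose-withholding rule, one paragraph before the suspension sentence, starts at Grade 2 and is open above. The suspension sentence is closed at Grade 4.

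**Step 3. Which fatal cases are left out.** A case graded 3 or 4 before death has already triggered the suspension. What remains is a renal death for which Grade 5 is the only grade ever assigned.

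The visit schedule leaves room for this. Dosing is on Days 1 and 4 of Weeks 1 to 3, which are cycle days 1, 4, 8, 11, 15 and 18, with the next cycle starting on day 29. The gaps are 3, 4, 3, 4, 3 and 29 − 18 = 11 days. From Cycle 3, Table 5-2 schedules chemistry on Day 1 only, 28 days apart. These are nominal intervals: dosing may move by a day either way, and cycles with a scan add a Week 4 visit.

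**Step 4. Whether another rule forces a pause in the remaining case.**

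- *DLT rules.* Under Section 6.1.1 a possibly related death is not a DLT, because probable or definite relation is required. Under Section 9.0 it would be one, because no attribution condition is stated. The conclusion is the same on either reading. A first DLT expands the cohort to at most 6 patients. A second closes that dose level and sends later patients to a lower dose. Neither suspends enrolment, and neither applies after Cycle 1.
- *Cohort 5.* The text reads "There are 10 patients in this cohort. These patients will be treated with CPI-613 for 5 days during the pre-Cycle 1 week", and no DLT rule follows for these patients.
- *STRC (Appendix B).* Every Grade 5 event, whatever its attribution or expectedness, requires a telephone call to a clinical member and a form within 24 hours. The form asks whether the protocol should be suspended. The committee's right to suspend is stated for the case where it disagrees with the investigator. Review is mandatory; suspension is not.
- *Sponsor and IRB.* Related, unexpected serious events go to the sponsor within 7 days (Section 8.1). Unanticipated problems go to the IRB within 7 calendar days, and the investigator must ensure that reported risks "are reviewed to determine whether the report represents a change in the risks and/or benefits to study participants" (Section 8.3). These are notice and review duties, not holds.

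**Step 5. Cost of the wider trigger.** Section 9.0 says "We anticipate accruing one patient per month for this protocol". With an average month of 30.44 days, a one-week pause delays 7 / 30.44 = 0.23 patients.

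**The case against.** The strongest reply is that the remaining case is nearly empty. The clause speaks of the severity level of the event, not of what was written down first. The log labels Grade 4 as life-threatening, and a patient who dies of acute renal failure will ordinarily have had life-threatening renal failure beforehand. On that reading the trigger was met before death. In addition, every Grade 5 event reaches the STRC within 24 hours, with the suspension question on the form. Enrolment would then continue only if the investigator and the committee both saw no need to stop.

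Much of this stands, and it makes the point a small one. It does not remove it. A literal reader may still treat a death graded only 5 as outside the clause, and the STRC route replaces an automatic hold with a judgement. For non-fatal renal failure the authors chose an automatic hold, so the plan gives the fatal case weaker protection than the lesser one.

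A reader might infer more than this. The documents do not support the view that renal deaths in general leave enrolment open, because a case earlier graded 3 or 4 already triggers the suspension. Nor can it be said flatly that a possibly related renal death is never a DLT, because Section 9.0 states no attribution condition. It would also go too far to conclude that every possibly related death needs an automatic hold. That would be a new rule for non-renal events, and the gap in this sentence does not call for it.

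**Conclusion.** The point holds in a narrow form. As worded, Section 6.2 guarantees an enrolment pause for non-fatal severe renal failure, but not for a renal death that is only ever graded 5, and no other rule guarantees one. This rests on a literal reading of the grade range and on the case not having been graded 3 or 4 earlier.

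The case is likely rare. The documents give no rate of fatal renal failure, so its probability cannot be stated. No analysis, dose decision or care of a patient already on treatment is affected. It reads as a drafting slip: a minor matter that is worth correcting because the correction is so cheap.

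**What to change.** In the enrolment-suspension sentence of Section 6.2, replace Grade 3 or 4 with Grade 3 or higher. Leave the other Grade 3 or 4 wording in that section as it is, since it governs dosing of surviving patients. Leave the STRC procedure unchanged. The escalation scheme, of which Section 9.0 says "This scheme has been discussed/proposed by the FDA", also needs no change.

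The cost is one phrase in an amendment and, if the case arises, the same temporary suspension already accepted for Grade 3 or 4. The plan does not state how long that suspension lasts; the delay is the 0.23 patients per week worked out above.
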